*** ONLY EVENTS WITH AN ONSET DATE \geq START DATE ARE CONSIDERED**
ONLY FOR SUBJECTS WITHOUT AN EVENT WITH AN ONSET DATE \geq START DATE
^ E.G. IN CASE OF AN INTERIM ANALYSIS
\$ DATE OF SYMPTOM ONSET OF A VIROLOGICALLY-CONFIRMED COVID-19 CASE. AFTER SUCH A CASE, SUBJECT CAN NO LONGER BE CONSIDERED AN "ASYMPTOMATIC" SUBJECT.
€ XXX IS A PLACEHOLDER FOR THE ANALYZED VARIANT/CLUSTER (E.G. ALPHA)
§ 18TH JUN-2021 CUT-OFF DATE FOR PRIMARY EFFICACY ANALYSIS

10.14 Age Group

Subjects are assigned to age groups “18 to 60 years” and “ \geq 61 years” based on their age recorded in IWRS. If age is missing in IWRS then age group is assigned based on the age derived from year of birth recorded in IWRS and date of first informed consent (age = year of date of first informed consent – year of birth).

11.0 Interim Analyses

Two interim analyses are performed for this trial by an unblinded independent statistician with no previous involvement in the trial and reviewed by the DSMB when 56 and 111 cases of COVID-19 (meeting the primary efficacy case definition) are observed. These analyses aim to assess early high efficacy or futility on the primary efficacy endpoint of COVID-19 cases of any severity and are done on the EAS only. The safety data that is available at this time point is be described.

For the analysis of early demonstration of high efficacy or futility, cumulative O’Brien-Fleming type error-spending-function [1] is used to provide statistical stopping rules for high efficacy (α -boundaries) and futility (β -boundaries) for the interim analyses, based on the information accumulated until that specific interim stage.

At the interim stage, if the p-value for the test of the primary endpoint of COVID-19 cases of any severity is lower than the α -boundary, a high level of efficacy for CVnCoV is declared. Conversely, demonstration of futility occurs if the p-value is higher than the β -boundary.

The interim analyses are planned to occur when 56 and 111 cases of any severity, meeting the primary case definition have been observed. The analysis of this primary endpoint is performed as described in detail in Section 12.6.1 and Section 12.6.2.1. If the interim analyses are performed exactly after 56/111 cases have been reported, a 1-sided p-value lower than 0.00015/0.00707 (i.e. LL of the 2-sided

99.97%/98.586% CI > 30%) for the test on the primary endpoint of COVID-19 cases of any severity leads to the conclusion of high efficacy, while a 1-sided p-value higher than 0.66345/0.12356 results in the demonstration of futility. Otherwise, the final primary efficacy analysis is performed at 160 cases.

Table 12 below shows the boundaries for demonstrating high efficacy or futility based on 56 and 111 cases, calculated on a one-sided p-value scale using the cumulative error spending function.

Table 12: Decision rules for interim and final analyses based on 56, 111 and 160 cases

	Interim Analysis 1	Interim Analysis 2	Final Analysis
Number of cases	56	111	160
Efficacy α -Boundary on p-value scale (1-sided)	0.00015	0.00707	0.02281
Futility β -Boundary on p-value scale (1-sided)	0.66345	0.12356	NA

It should be noted that the actual boundaries used for decision making depend on the exact number of cases accrued at the time of each analysis. At the time of the interim analysis, actual boundaries are re-derived based on the actual number of cases accrued and are displayed in the IA outputs. The boundaries are applied in a non-binding way as there may be other factors that are part of the decision-making process.

A list of Tables, Figures and Listings (TFL) that is prepared for the IA can be found in a separate document CV-NCOV-004 Statistical Analysis Plan – Appendix 4 List of TFLs.

12.0 Statistical Methods

Unless otherwise noted, categorical variables are summarized using counts and percentages. Percentages are presented with one decimal place, except for 100% which is displayed without any decimal places and percentages are not displayed for zero counts. Continuous variables are summarized using the number of observations (n), mean, median, SD, 1st Quartile (Q1), and 3rd Quartile (Q3), minimum and maximum values. Mean, median, Q1 and Q3 are presented to 1 decimal more than original data. SD is presented with 2 decimals more than original data. Minimum and maximum match the decimal points in the original data. The maximum number of decimals is 4, unless otherwise stated.

In general, for the blinded study phase, all data summaries are presented overall and by vaccine group. Summaries are further repeated by age group (18 to 60 years and ≥ 61 years) and vaccine group. Efficacy outputs do not have an overall column presented. Selected outputs are additionally presented using further subsetting of the data. This is specified explicitly in the respective sections. Data summaries for the OL-phase are generally presented by cohort, unless otherwise stated.

If not stated otherwise, p-values from statistical tests are two-sided and CIs are calculated using a 95% confidence level.

The factors used for stratification of randomization are age group and country. The primary and key secondary efficacy analyses are not adjusted for these factors, but the analyses are repeated by age group (18 to 60 years and ≥ 61 years) and by country separately. The sensitivity analyses for the primary endpoint using time to event methodology includes both stratification factors in the statistical model.

No imputation of missing data other than that described in Section 10.3 is performed.

All data collected during this trial is displayed in data listings, unless otherwise specified. Screening failures are excluded from all listings and tables if not otherwise stated. Listings include all relevant assigned/derived variables. If not explicitly stated, listings do not show imputed data, but present data as reported.

All data summaries and tabulations are prepared using SAS® Version 9.4 or higher.

12.1 Subject Disposition

A summary of enrollment by region (Latin America vs Europe), country and site is provided for all randomized subjects. This summary is repeated on the OL Set.

The number and percentage of subjects who prematurely withdrew from treatment, prematurely withdrew from the trial before entering the OL phase, rolled over to the OL phase, prematurely withdrew from the trial during the OL phase and a breakdown of the corresponding reasons for treatment withdrawal and early trial discontinuation (summarized separately for blinded and OL phase) is provided.

The number and percentage of subjects randomized and treated is presented with the number and percentage of subjects included in each analysis set. Reasons for exclusion from each analysis set is not tabulated, but listed.

The number of subjects whose data is censored due to unblinding and/or AV application are provided for unblinding and/or AV use before dose 2 and after dose 2. The output is provided for the SAS and for all randomized subjects. A separate listing is provided indicating the date a subject was unblinded / received an AV. Subjects who have received an AV without being unblinded are also included in that listing.

The number and percentage of subjects who were not stratified correctly is presented along with the number of subjects who received an incorrect vaccine at first and/or second vaccination. The summary is done for all randomized subjects. These subjects are also listed.

12.2 Demographic and Baseline Characteristics

The following demographic data collected at baseline is summarized for the SAS, EAS and OL Set. The data used for the OL Set summary is the same as for SAS and EAS (ie. the data collected at Day 1):

- Age at first informed consent (years),
- Age group (18 to 60 years / \geq 61 years),
- Gender (Female / Male / Undifferentiated / Unknown),
- Ethnicity (Hispanic or Latino / Not Hispanic or Latino / Not Reported / Unknown),
- Race (American Indian or Alaska Native / Asian Indian/ Black or African American / Chinese / Filipino / Japanese / Korean / Native Hawaiian or Pacific Islander / Vietnamese / White / Other / Not reported / Unknown),
- Baseline and Visit Day 43 serology status (Seronegative / Seropositive), see Section 10.6.1 for details.
- Baseline and Visit Day 43 serology status, overruled by independent committee adjudication if available (Seronegative / Seropositive), see Section 10.7.6 for details.
- Height (cm),
- Weight (kg),
- Body Mass Index (BMI) (kg/m^2).
- Smoking Status (Never / Current / Former)
- Duration of Smoking (within the group of former and current smokers)

12.3 Medical and Surgical History

Medical/surgical history is coded using the MedDRA Version 23.1 or higher and is summarized by Primary SOC and PT for the SAS and EAS. Medical/surgical history is listed for the SAS.

The number and percentage of subjects with any co-morbidity and a breakdown of the corresponding co-morbidities is provided for the SAS and EAS.

12.4 Trial Treatment

12.4.1 Trial Vaccine Exposure

A summary of doses administered, including reasons for doses not administered is provided for the SAS.

12.4.2 Prior and Concomitant Medications and Vaccinations

Prior and concomitant medications and vaccinations are coded using World Health Organization Drug Dictionary (WHODRUG), Version September 2020 Global B3 or higher, and are summarized based on the SAS and EAS. The summary of concomitant medications/vaccinations is repeated on the OL Set.

Concomitant medications/vaccinations (see Section 10.4) are summarized by Anatomical Therapeutic Chemical (ATC) level 1 and WHODRUG PN as the number and percentage of subjects taking at least one medication within each medication group and subgroup.

Prior medications/vaccinations (see Section 10.4) are summarized by ATC level 1 and WHODRUG PT as the number and percentage of subjects taking at least one medication within each medication group and subgroup.

12.5 Important Protocol Deviations

Per PRA processes, protocol deviations data are entered into PRA system of records (PSO). The trial team and the Sponsor conduct ongoing reviews of the deviation data from PSO and the resulting set of evaluable subjects throughout the trial, adjusting the deviation criteria as seems appropriate.

Protocol deviation data are reviewed prior to each formal analysis (i.e. interim analyses or final analyses) and important deviations leading to elimination of subjects from analysis sets are identified. Detailed definitions and further guidance on programmatic approaches for identification of protocol deviations and/or other criteria leading to exclusion from the analysis sets are provided in an Appendix to the SAP (see Appendix 5). The detailed definitions of important protocol deviations leading to elimination of subjects from analysis sets are provided in the final version of the SAP and/or in the final signed minutes of the data review meetings prior to each formal analysis and prior to database lock.

A summary of important subject-level protocol deviation data (conjoinedly for the blinded and the OL phase) is created based on the SAS, displaying the number and percentage of subjects with any important protocol deviations and broken down by type of deviations.

Site- and subject-level protocol deviation data is listed conjoinedly for the blinded and the OL phase.

12.6 Efficacy Analyses

12.6.1 Hypothesis Testing Strategy and Multiplicity

The overall 2-sided significance level of 5% is applied to the primary endpoint (or equivalently, a 1-sided 2.5% level of significance).

The primary endpoint of COVID-19 cases of any severity is evaluated at two interim analyses (see Section 11.0) and - if the trial is not stopped due to futility or early high efficacy at either of the interim analyses - at the final primary efficacy analysis (when 160 cases have accrued). A cumulative O'Brien-Fleming type error spending function [1] is utilized to provide statistical stopping rules for the interim analyses. The related outputs are not planned to be re-run at the EOT analysis. Due to the fact that the unblinding dates for site AR009 were only corrected after the final delivery for the primary analysis was done it might nevertheless be decided to re-run some of the related outputs together with the EOT analysis.

Assuming the interim analyses are based on 56 and 111 cases and the final primary efficacy analysis based on 160 cases, the two-sided significance level to be considered for the primary analysis of the first primary endpoint of COVID-19 cases of any severity is 4.562% (based on the error spending function used

for the interim analyses). This level may change depending on the number of cases accrued at the time of each analysis.

Analysis of the key secondary efficacy endpoints is performed according to a conditional hierarchical testing procedure using the order defined in endpoints sections, see Section 9.2.1. Moreover, efficacy of CVnCoV in regard to the key secondary efficacy endpoints is demonstrated only if there is successful demonstration of the primary efficacy objective. Otherwise, these endpoints are analyzed as exploratory endpoints without success criteria testing.

The analyses of the key secondary endpoints are performed at the final primary efficacy analysis only, using a two-sided 5% significance level. They are not planned to be re-run at the EOT analysis. Due to the fact that the unblinding dates for site AR009 were only corrected after the final delivery for the primary analysis was done it might nevertheless be decided to re-run some of the related outputs together with the EOT analysis.

For any analyses requiring the serostatus at baseline or Visit Day 43 the information of the adjudication of COVID-19 cases is used, if available (Section 10.7.6). Otherwise the information of the N protein blood samples taken at baseline and Visit Day 43 is used (Section 10.6.1).

12.6.2 Primary Efficacy Endpoint Analysis

12.6.2.1 Primary Efficacy Analysis

The primary endpoint in this trial is the occurrence of first episodes of virologically-confirmed cases of COVID-19 of any severity meeting the case definition for the primary efficacy analysis (see Section 10.7.4).

From the number of occurrences of COVID-19 cases in each vaccine group, the VE corresponding to the endpoint is calculated as follows:

$$VE = 1 - \frac{p}{1-p} * \frac{1}{r}$$

Thereby, p denotes the proportion of cases coming from the CVnCoV group among all cases and r is the ratio of total follow-up time of subjects in the CVnCoV group over the total follow-up time of subjects in the placebo group (see Section 10.13).

The statistical hypothesis for the primary efficacy endpoints is:

$$H_{0A}: VE \leq 30\% \text{ vs. } H_{1A}: VE > 30\%$$

Or, equivalently:

$$H_{0A}: p \geq \frac{0.7}{\frac{1}{r} + 0.7} \text{ vs. } H_{1A}: p < \frac{0.7}{\frac{1}{r} + 0.7}$$

Thereby, A refers to the endpoint of COVID-19 cases of any severity.

It should be noted that the above reduces to

$$H_{0A}: p \geq 0.4118 \text{ vs. } H_{1A}: p < 0.4118,$$

if the total follow-up time is the same in both groups, i.e. if r equals 1.

For the primary analysis, the above hypotheses are tested via an exact test for Binomial proportions on p. with an overall 2-sided significance level of 5% (or equivalently, a 1-sided 2.5% level of significance).

Given the IA stopping rules for the primary endpoint of COVID-19 cases of any severity, if the final primary efficacy analysis is performed at 160 cases, the tests are performed with a 1-sided 2.281% level of significance, to keep the type I error rate for this endpoint at 5% (2-sided). See also Section 11.0 for further details.

An exact two-sided 95.438% Pearson-Clopper CI for p is calculated. From this, the LL and Upper Limit (UL) of the 95.438% CI for the VE is calculated from the UL and LL of the CI for p as:

$$LL_{VE} = 1 - \frac{UL_p}{(1 - UL_p) * r}; \quad UL_{VE} = 1 - \frac{LL_p}{(1 - LL_p) * r}$$

Efficacy on this primary endpoint is demonstrated at the final primary efficacy analysis if the UL of the 95.438% CI for p is below 0.4118. Note that this is equivalent to the LL of the 95.438% CI for the VE being above 30%.

The trial is successful if efficacy is demonstrated on the primary endpoint.

The following is presented for the analysis of the primary endpoint:

- Number and percentage of subjects with a respective COVID-19 case (any severity) meeting the case definition for the primary efficacy analysis in each vaccine group,
- Total follow-up time (years) in each vaccine group,
- Calculated proportion of cases coming from the CVnCoV group among all cases (p),
- Ratio of total follow-up time of subjects in the CVnCoV group over the total follow-up time of subjects in the placebo group (r),
- Estimated VE based on p and r,
- 1-sided p-value from the exact Binomial test for the above hypotheses on p,
- 95.438% CIs for p and VE for the primary endpoint of COVID-19 cases of any severity.

The primary analysis set for the primary analysis is the EAS. Any repeated analyses using an analysis set other than EAS or analyses by subgroup present 95% CIs and no p-values are presented.

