3.1.4 HERALD Phase 2b/3 Results

The HERALD final efficacy analysis on 25,062 subjects meeting the inclusion criteria for the primary analysis, including 228 confirmed adjudicated COVID-19 cases, has demonstrated:

- An overall CVnCoV vaccine efficacy (VE) of 48% (p=0.01600, 95.826% CI 31.0-61.4%) for all age groups against COVID-19 of any severity, including single non-respiratory mild symptoms.
- Significant protection was also shown among subjects in the age group of 18 to 60 years, with an efficacy of 52.5% (95% CI 36.2-64.8%) against disease of any severity and across the 15 identified strains; protection against moderate to severe disease was 77% (95% CI 51.8-90.4%).
- In subjects over 60 years (21 cases, 9% of the analyzed COVID-19 cases), the available data did not allow a statistically significant determination of efficacy. Therefore, CureVac reassessed the benefit/risk by age group and advised the investigators to discuss administration of an AV to trial subjects ≥ 60 years.
- Overall, the data confirm the favorable safety profile of CVnCoV.

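### SAP v5.0 states the final primary criterion only at the 160-case level (95.438%), although the 228-case analysis was reported at 95.826% and a re-run is left open

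*SAP*

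**What the plan says.** SAP 12.6.1 sets the overall error: "The overall 2-sided significance level of 5% is applied to the primary endpoint (or equivalently, a 1-sided 2.5% level of significance". It is spent through an O'Brien-Fleming "type error spending function [1] is utilized to provide statistical stopping rules for the interim analyses". The two-sided 4.562% given there for the final test is introduced by "Assuming the interim analyses are based on 56 and 111 cases and the final primary efficacy analysis based on 160 cases", and followed by "This level may change depending on the number of cases accrued at the time of each analysis".

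SAP 12.6.2.1 ties the one-sided 2.281% test level to a final analysis at 160 cases. Three later statements in that section carry no such condition:
- the interval: "An exact two-sided 95.438% Pearson-Clopper CI for p is calculated";
- the success rule, which compares the upper limit of that interval for p with 0.4118;
- the output list: "95.438% CIs for p and VE for the primary endpoint of COVID-19 cases of any severity".

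Protocol 3.1.4 gives the outcome of the final analysis, based on 228 adjudicated cases: "An overall CVnCoV vaccine efficacy (VE) of 48% (p=0.01600, 95.826% CI 31.0-61.4" (percent).

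SAP v5.0 is dated 10 March 2022, after that analysis. Of the primary and key secondary outputs it says that, because the AR009 unblinding dates were corrected late, "it might nevertheless be decided to re-run some of the related outputs together with the EOT analysis".

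**The concern.** A group-sequential final level belongs to a particular set of looks. The SAP prints the level for a 160-case final look as the operative criterion, while the protocol shows that the 228-case analysis used another. The figure 95.826% does not appear in the SAP, and nothing in it lets a reader derive that figure.

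This matters because the result is close to the margin (lower limit 31.0% against 30%) and a re-run is left open. The AR009 correction changes unblinding dates, hence censoring, membership of the efficacy analysis set, case counts and the follow-up ratio r. SAP 6.1 says that v5.0 was written by an unblinded team. The level for a re-run should therefore be settled in writing beforehand, not chosen between two printed figures.

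**Working it through.** **1. The plan's own figure.** Inputs (SAP 11.0 and 12.6.1): one-sided 0.025, Lan-DeMets O'Brien-Fleming spending, looks at 56/111/160. Spending function: 2 − 2Φ(2.2414/√t), with t = 56/160, 111/160 and 1. Result: 0.00015, 0.00707, 0.02281, matching SAP Table 12. Two-sided confidence: 1 − 2 × 0.02281 = 95.438%. The exact binomial cut-offs at p0 = 0.7/1.7 = 0.4118 are 9/56, 32/111 and 53/160, as in Protocol Table 10.

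**2. The level reported.** (1 − 0.95826)/2 = 0.02087.

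**3. The level for a final look at 228.** It depends on a convention the SAP does not state:

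| Convention | Second look | Final one-sided level |
|---|---|---|
| Spend on planned 160, remainder at the final look | 111 | 0.02106 |
| Same | 112 | 0.02090 |
| Same | 113 | 0.02074 |
| Spend on actual information (56/111/228) | 111 | 0.02457 |

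The reported 0.02087 lies close to the planned-160 values. It cannot be confirmed, because the realised interim counts are not given. Under that convention, with interims at 56 and 111, using 0.02281 at 228 gives an overall one-sided error of 0.0266 instead of 0.025.

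**4. Arm split and r (not in the documents).** VE = 1 − k/(228 − k)/r, with null proportion p0 = 0.7/(1/r + 0.7). Solving for the reported VE, interval and p leaves only two pairs:
- k = 82, r about 1.085: 1 − (82/146)/1.085 = 48.2%;
- k = 83, r about 1.105: 1 − (83/145)/1.105 = 48.2%.

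At these values the lower limit is 31.0% at 95.826% and 31.4% at 95.438% (31.3% with r rounded as shown). The result passes at both levels.

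**5. Where the two levels disagree.** At r = 1 and 228 cases, 78 vaccine cases pass both (p = 0.0185) and 79 fail both (p = 0.0257), so no count separates them. At the back-solved r the cut-offs are 83 against 82 (k = 82), or 84 against 83 (k = 83). Over 100 to 300 cases and r from 0.8 to 1.25 they never differ by more than one case.

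The AR009 correction can only remove cases or follow-up. With r held fixed:

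| Cases removed | p | Verdict |
|---|---|---|
| 1 placebo | about 0.0183 | passes both |
| 2 placebo | about 0.0209–0.0210 | lower limit 30.3% at 95.438%; 29.97–29.98% at 95.826% with r rounded to 1.085 and 1.105 |
| 3 placebo | about 0.024 | fails both |
| 2 placebo, 1 vaccine | about 0.0172 | passes both |

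With r solved to more decimals from p = 0.01600, the second row becomes 30.00% (k = 82) and 29.99% (k = 83). That case is on the line, not a clear failure.

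**6. The 0.4118 threshold.** It equals 0.7/(1/r + 0.7) only at r = 1. At r about 1.085 the threshold is 0.7/(0.9217 + 0.7) = 0.432; at 1.105 it is 0.436. The 95.438% upper limit for p is 0.427 (k = 82) or 0.431 (k = 83). Read literally, the 0.4118 rule would fail a result whose VE lower limit exceeds 30%.

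**The case against.** A reader might infer that the SAP hard-codes the wrong level. It does not. The sentence before the interval statement is conditional on 160 cases, 12.6.1 lets the level change, and SAP 11.0 and Protocol 10.3.8 tie boundaries to the exact counts, the protocol for interim and final looks alike. Reporting at 95.826% shows that the level was in fact adjusted. This stands, but none of these clauses gives the resulting level, and the re-derivation that SAP 11.0 spells out concerns the interim analyses.

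The re-run may never happen. SAP 6.2 says no efficacy analyses are performed at end of trial, and 12.6.1 calls a re-run unplanned. That lowers the urgency, but 12.6.1 still leaves it open.

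A reader might also infer that any change of one or two cases flips the verdict. Moving one case from placebo to vaccine would split the levels (lower limit 30.1% at 95.438%, 29.7% at 95.826%). But efficacy sets are analysed as randomised and SAP Table 10 only keeps dates or moves them earlier, so this correction cannot move a case between arms. Of the removals tested, only the loss of two placebo cases splits the levels, and then marginally.

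Finally, calling 0.02281 too lenient rests on an inferred convention. Under actual-information spending (0.02457) it would be conservative. That also stands.

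**Conclusion.** The point holds as a gap in the stated decision criterion. SAP v5.0 prints a level that the protocol shows was not the one used at 228 cases, and it omits what is needed to derive the right one. The documents do not support reading this as a flaw in the reported efficacy conclusion: p = 0.01600 is below both 0.02087 and 0.02281.

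The practical size is small: at most one critical case, and none at r = 1. It could matter only in a borderline re-run. The sensitivity figures assume an arm split and r back-solved from rounded results, with r unchanged by the correction; the 0.0266 error rate assumes spending on the planned 160 cases. The 0.4118 defect is separate and applies whenever r differs from 1.

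**What to change.** In SAP 12.6.1 and 12.6.2.1 (test level, interval, success rule and output list):
- Label 2.281% / 4.562% / 95.438% as illustrative for looks at 56/111/160.
- State the level used for the 228-case analysis (95.826%, one-sided 0.02087), the realised interim counts, and the spending convention, including how alpha is spent beyond 160 cases.
- State that any AR009 re-run uses a level derived by that same convention from the re-run case count, with the interim alpha already spent held fixed. Carrying 95.826% over unchanged would repeat the problem if the count moves.
- Replace 0.4118 in the success rule with 0.7/(1/r + 0.7).

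The cost is wording, plus retrieving the interim counts; SAP 11.0 says the re-derived interim boundaries are displayed in the interim outputs. The downside is a slightly stricter stated criterion than 95.438%.

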8.7.1 Sample Size Considerations for the Primary Objective

A group sequential design with two interim analyses for demonstrating a high level of efficacy or reaching futility is planned using O'Brien and Fleming type error-spending-function [1] and the sample size is based on the test for one single proportion (i.e. the proportion of cases coming from CVnCoV group among all cases). The interim analyses for high efficacy or futility based on the primary endpoint of COVID-19 cases of any severity was to be performed once 56 and 111 cases have been accrued (approximately 35% and 69% of the final number of cases).

With a 2-sided alpha of 5%, a total of 160 COVID-19 cases of any severity (meeting the primary efficacy case definition for COVID-19 cases of any severity) are needed at final primary efficacy analysis, to have a power of 90% to demonstrate the VE is above 30% based on the lower bound of the confidence interval (CI) for VE when assuming that the VE under the alternative hypothesis is 60%. Note that this is equivalent to demonstrating that the proportion of cases coming from CVnCoV group is below 0.4118 based on the upper bound of the CI for the proportion when assuming that the proportion under the alternative hypothesis is equal to 0.2857.

Assuming an incidence rate of COVID-19 of 0.15% per month in placebo subjects, an overall non-evaluable rate of 20% (corresponding to subjects excluded from the Efficacy Analysis Set and drop-outs) and a VE of 60%, 36,500 subjects enrolled over approximately 3 months (18,250 per vaccine group) accrue 160 COVID-19 cases of any severity around 9 months after the first vaccination. A lower incidence rate, a longer enrollment duration, or a higher non-evaluable rate or VE delay the acquisition of the 160 cases and the time of final primary efficacy analysis.

Subjects are randomized to receive either CVnCoV or placebo in a 1:1 ratio, stratified by country and age group (18 to 60 and \geq 61 years of age).

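### SAP 12.6.2.1 fixes the final success threshold for p at 0.4118, which matches a VE lower limit of 30% only when both arms have equal person-time

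*SAP*

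**What the plan says.** SAP 12.6.2.1 first states the null hypothesis as VE of 30% or less. It then restates it for p, the share of cases in the CVnCoV arm, with threshold 0.7/(1/r + 0.7), where "r is the ratio of total follow-up time of subjects in the CVnCoV group" over that in the placebo group. It adds that the threshold becomes 0.4118 "if the total follow-up time is the same in both groups, i.e. if r equals 1". Both VE confidence limits in that section are computed with r.

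The decision sentence then omits r. Efficacy "is demonstrated at the final primary efficacy analysis if the UL of the 95.438% CI for p is below 0.4118", followed by: "Note that this is equivalent to the LL of the 95.438% CI for the VE being above 30" per cent. The section next makes trial success depend on this result.

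SAP 8.7.1 uses the same constant for planning, describing the aim as "demonstrating that the proportion of cases coming from CVnCoV group is below 0.4118" "when assuming that the VE under the alternative hypothesis is 60" per cent.

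Protocol 10.3.5.1 defines success for cases of any severity on the VE scale (lower limit above 30%) and warns that the case-split rule can change when r is not 1. Protocol 3.1.4 reports 228 adjudicated cases and the result "VE) of 48% (p=0.01600, 95.826% CI 31.0-61.4" per cent. It gives no case split, no r and no limits for p.

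**The concern.** The decision sentence and its equivalence note agree only at r = 1. At any other r, a final analysis can pass one and fail the other, so the SAP contains two confirmatory rules under one name.

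Unequal person-time was foreseeable. SAP 10.11 and 10.13 end efficacy follow-up the day after unblinding or receipt of an authorized vaccine, and nothing forces that loss to be equal between arms.

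At stake is the definition of success. Under SAP 12.6.1 it is also the gate to formal testing of the three key secondary endpoints.

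**Working it through.** **Inputs.** Margin VE 30%, alternative VE 60%, 160 cases (SAP 8.7.1). Final one-sided level 0.02281 and 95.438% Clopper-Pearson interval (SAP 12.6.2.1). Success at 53 or fewer of 160 when r = 1 (Protocol 10.3.5.1). Reported result from Protocol 3.1.4. All values of r below are assumed or inferred.

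**1. The plan's own figure at r = 1.** p0 = 0.7/1.7 = 0.4118 and p1 = 0.4/1.4 = 0.2857.
- P(X ≤ 53 | 160, p0) = 0.0224, within 0.02281. P(X ≤ 54) = 0.0327, which is not.
- The upper limit for p is 0.4115 at 53 cases and 0.4179 at 54.
- VE at 53/107 is 1 − 53/107 = 50.5%.

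The plan's 53/160 and 50.5% reproduce. Exact single-look power is 91.2%, against the stated 90%.

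**2. The claimed equivalence.** The SAP's limit is LL(VE) = 1 − UL_p / ((1 − UL_p) × r). Setting UL_p = 0.7/1.7 gives UL_p/(1 − UL_p) = 0.7, so LL(VE) = 1 − 0.7/r.

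| r | LL(VE) when UL_p = 0.4118 |
|---|---|
| 0.90 | 22.2% |
| 0.95 | 26.3% |
| 1.00 | 30.0% |
| 1.05 | 33.3% |
| 1.10 | 36.4% |

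**3. Consequence at 160 cases, assumed r.** Use p0(r) = 0.7r/(1 + 0.7r) and p1(r) = 0.4r/(1 + 0.4r), exact binomial, final look only. The written rule stays at 53 or fewer.
- Chance of success at VE 30%: 2.2% at r = 1; 8.7% at r = 0.9 (p0 = 0.63/1.63 = 0.3865); 0.5% at r = 1.1 (p0 = 0.77/1.77 = 0.4350).
- Power at VE 60%: 91.2% at r = 1 and 78.7% at r = 1.1. The r-correct rule at r = 1.1 allows 56 of 160 and keeps 90.3%.

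**4. Back-solving the reported result.** For each CVnCoV count x out of 228, compute the Clopper-Pearson interval at 95.826% and convert it to VE. The ratio (1 − LL)/(1 − UL) does not depend on r, so it identifies x; r then follows from the limits. Only two splits round to 48% (31.0 to 61.4).

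| Split | r | UL_p | r-correct threshold | One-sided p, r-correct | One-sided p against 0.4118 |
|---|---|---|---|---|---|
| 82/146 | about 1.085 | 0.428 | 0.432 | 0.016 | 0.062 |
| 83/145 | about 1.105 | 0.433 | 0.436 | 0.016 | 0.081 |

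Check for 82/146: VE = 1 − (82/146)/1.085 = 48.2%, and LL = 1 − (0.4282/0.5718)/1.085 = 31.0%.

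Equal person-time does not fit: 78/150 at r = 1 gives VE 48.0% but limits of 30.5 to 61.4. With 228 cases the written rule allows at most 78 in the CVnCoV arm. Applying the literal 95.438% level to the two fitted splits gives UL_p of 0.427 or 0.431 (fails 0.4118) and LL(VE) of 31.3 to 31.4% (passes 30%).

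**The case against.** The best defence is that the intended rule is clear from context. The null hypothesis is written on the VE scale and then with r, the restriction of 0.4118 to r = 1 is stated a few lines earlier, the VE limits carry r, and the exact test is of those hypotheses. The equivalence note itself shows that a VE lower limit above 30% was meant, and Protocol 10.3.5.1 says so directly. The SAP's list of primary outputs already includes r. All of that stands. It makes this a dropped condition and not a deliberate second criterion, but the sentence that declares success remains false as written.

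A reader might infer that the trial failed its own prespecified criterion. The documents do not support that. The split, r and UL_p are unreported, and the failure in step 4 comes from limits rounded to 0.1 points. It also depends on the confidence level: at 95.438% the same rounded figures fit 76 or 77 cases with r about 0.966 or 0.984, giving UL_p of 0.400 or 0.404, which passes 0.4118. The stated level of 95.826% and the reported p = 0.01600 favour the 82 or 83 reading, because 76 or 77 would give p of about 0.0177. That makes the inference credible without making it a reported fact.

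A reader might also infer that the type I error was inflated. The 8.7% needs r = 0.9, which is an assumption; the back-solved r is above 1, where the written rule is conservative.

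**Conclusion.** The point holds. The success sentence in SAP 12.6.2.1 and its equivalence note are correct only at r = 1, and otherwise contradict the SAP's own null hypothesis and Protocol 10.3.5.1. This follows from the SAP's formulas alone. The size depends on r: across r from 0.9 to 1.1 the VE bound actually required runs from 22.2% to 36.4%.

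That the literal rule would fail on the reported data, while the VE rule passes, is an inference. It assumes that the reported interval used the SAP's Clopper-Pearson method at 95.826%. Agreement with p = 0.01600, which the search did not use, supports it. The same agreement indicates that the r-adjusted test was applied, so the reported VE conclusion is not undermined; the defect is in the written rule. The 0.4118 in SAP 8.7.1 is a legitimate planning value for r = 1.

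The wording still matters. SAP 12.6.1 allows some primary and key secondary outputs to be re-run after the correction of unblinding dates at site AR009. That correction can change person-time and hence r, and the reported lower limit is only one point above 30%.

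**What to change.** Replace the success sentence and the equivalence note in SAP 12.6.2.1 with:

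*Efficacy is demonstrated if the LL of the CI for VE, at the level re-derived for the actual number of cases, is above 30%; equivalently, if the UL of the CI for p is below 0.7/(1/r + 0.7), with r the observed follow-up ratio.*

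Limit 0.4118 to the planning case r = 1 in SAP 8.7.1 and Protocol 10.1.1. SAP 6.1 states that version 5.0 was written by an unblinded team, so record the change as a correction restoring agreement with the SAP's null hypothesis and Protocol 10.3.5.1, to apply to any re-run after the site AR009 correction.

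The cost is one sentence. No new data or outputs are needed, since p and r are already among the planned primary outputs.
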